APPENDIX I: PERFORMANCE STATUS SCALES/SCORES

Karnofsky		Lansky	
Score	Description	Score	Description
100	Normal, no complaints, no evidence of disease	100	Fully active, normal.
90	Able to carry on normal activity, minor signs or symptoms of disease.	90	Minor restrictions in physically strenuous activity.
80	Normal activity with effort; some signs or symptoms of disease.	80	Active, but tires more quickly
70	Cares for self, unable to carry on normal activity or do active work.	70	Both greater restriction of and less time spent in play activity.
60	Required occasional assistance, but is able to care for most of his/her needs.	60	Up and around, but minimal active play; keeps busy with quieter activities.
50	Requires considerable assistance and frequent medical care.	50	Gets dressed, but lies around much of the day; no active play, able to participate in all quiet play and activities.
40	Disabled, requires special care and assistance.	40	Mostly in bed; participates in quiet activities.
30	Severely disabled, hospitalization indicated. Death not imminent.	30	In bed; needs assistance even for quiet play.
20	Very sick, hospitalization indicated. Death not imminent.	20	Often sleeping; play entirely limited to very passive activities.
10	Moribund, fatal processes progressing rapidly.	10	No play; does not get out of bed.

This is NOT an all-inclusive list. Because the lists of these agents are constantly changing, it is important to regularly consult frequently updated medical references.

CYP3A4 substrates	Strong Inhibitors ¹	Moderate Inhibitors	Strong Inducers	Moderate Inducers
abemaciclib	atazanavir	aprepitant	apalutamide	bosentan
acalabrutinib ⁵	boceprevir	conivaptan	barbiturates	cenobamate
alfentanil ^{4,5}	clarithromycin	crizotinib	carbamazepine	dabrafenib
alprazolam ⁵	ceritinib	diltiazem	enzalutamide	efavirenz
amiodarone ⁴	cobicistat	dronedarone	fosphenytoin	eslicarbazepine
amlodipine	danoprevir/ritonavir	duvelisib	lumacaftor/ ivacaftor	etravirine
aprepitant/fosaprepitant	darunavir	erythromycin	mitotane	lorlatinib
atorvastatin	delavirdine	fedratinib	phenobarbital	modafinil
avanafil ⁵	elvitegravir/ritonavir	fluconazole	phenytoin	nafcillin
axitinib	grapefruit ³	fosamprenavir	primidone	
bortezomib	grapefruit juice ³	fosnetupitant	rifampin	
bosutinib ⁵	idelalisib	grapefruit ³	St. John's wort	
brexpiprazole	indinavir/ritonavir	grapefruit juice ³		
brigatinib	itraconazole	imatinib		
budesonide ⁵	ketoconazole	isavuconazole		
bupirone ⁵	lopinavir/ritonavir	lefamulin		
cabozantinib	nefazodone	letermovir		
calcium channel blockers	nelfinavir	mifepristone		
cisapride	paritaprevir/ritonavir/ ombitasvir +/- dasabuvir	netupitant		
citalopram/escitalopram	posaconazole	nilotinib		
cobimetinib ⁵	ritonavir	ribociclib		
colchicine ⁵	saquinavir	verapamil		
conivaptan ⁵	telaprevir			rifabutin
copanlisib	telithromycin			rifapentin
crizotinib	tipranavir/ritonavir			
cyclosporine ⁴	tucatinib			
dabrafenib	voriconazole			
dapsone				
darifenacin ⁵				
darunavir ⁵				
dasatinib ⁵				
dexamethasone ²				
diazepam				
dihydroergotamine				
docetaxel				
doxorubicin				
dronedarone ⁵				
ebastine ⁵				
eletriptan ⁵				
eliglustat ⁵				
eplerenone ⁵				
ergotamine ⁴				
erlotinib				
estrogens				
etoposide				
everolimus ⁵				
felodipine ⁵				
fentanyl ⁴				

gefitinib haloperidol ibrutinib ⁵ idelalisib imatinib indinavir ⁵ irinotecan isavuconazole ⁵ itraconazole ivacaftor ketoconazole lansoprazole lapatinib lomitinib ⁵ lorlatinib losartan lovastatin ⁵ lurasidone ⁵ macrolide antibiotics maraviroc ⁵ medroxyprogesterone methadone midazolam ⁵ midostaurin ⁵ modafinil naloxegol ⁵ nefazodone nilotinib nisoldipine ⁵ olaparib ondansetron osimertinib paclitaxel palbociclib pazopanib pimozide ⁵ quetiapine ⁵ quinidine ⁴ regorafenib rilpivirine ⁵ rivaroxaban ⁵ romidepsin saquinavir ⁵ sildenafil ⁵ simvastatin ⁵ sirolimus ^{4,5} sonidegib sunitinib tacrolimus ^{4,5} tamoxifen tadalafil ⁵ telaprevir temsirolimus				
--	--	--	--	--

teniposide tetracycline ticagrelor ⁵ tipranavir ⁵ tolvaptan ⁵ triazolam ⁵ trimethoprim vardenafil ⁵ vemurafenib venetoclax ⁵ vinca alkaloids zolpidem				
--	--	--	--	--

¹ Certain fruits, fruit juices and herbal supplements (star fruit, Seville oranges, pomegranate, ginkgo, goldenseal) may inhibit CYP 3A4 isozyme, however, the degree of that inhibition is unknown.

²Refer to [Section 7.5](#) regarding use of corticosteroids.

³The effect of grapefruit juice (strong vs moderate CYP3A4 inhibition) varies widely among brands and is concentration-, dose-, and preparation-dependent.

⁴Narrow therapeutic range substrates

⁵Sensitive substrates (drugs that demonstrate an increase in AUC of ≥ 5 -fold with strong inhibitors)

APPENDIX III-A: MEDICATION DIARY FOR TAZEMETOSTAT (ORAL SUSPENSION FORMULATION)

COG Patient ID: _____ Acc# _____ Institution : _____

Please do not write patient names on this form.

Instructions: Complete each day with the time and dose given for tazemetostat. Make note of other drugs and supplements taken in the Comments section below. Tazemetostat suspension should be given twice a day without regard to meals, with no less than 8 hours between each dose. Shake the bottle for one minute before you take tazemetostat, do not shake too much if there are bubbles wait for them to dissipate before measuring the dose.

Note: If multiple bottles are dispensed, daily shaking of all bottles is required to ensure the suspension stays properly suspended. Store your oral suspension in the refrigerator. If you vomit after taking tazemetostat suspension, the dose should NOT be repeated and the next dose should be taken at a regular scheduled time. This should be noted in the Comments section. Add the dates to the calendar below and return the completed diary to the study clinic at each visit (weekly during Cycle 1, and then after each treatment cycle).

EXAMPLE				AM Dose: Take 12 mL PM Dose: Take 12 mL	Comments (Describe any missed or extra doses, vomiting and/or bothersome effects.)
WEEK 1	Date	Time		Amount of oral suspension taken (mL)	
Day 1	2/15/19	8:30	AM	12	He felt nauseated an hour after taking the drug but did not vomit.
		8:30	PM	12	

Cycle #: _____ Start Date: ____/____/____ End Date: ____/____/____					
Dose Level: _____mg/m ² /dose					
WEEK 1	Date	Time	AM Dose: Take _____ mL PM Dose: Take _____ mL Amount of oral solution taken (mL)	Comments (Describe any missed or extra doses, vomiting and/or bothersome effects.)	
Day 1		AM			
		PM			
Day 2		AM			
		PM			
Day 3		AM			
		PM			
Day 4		AM			
		PM			
Day 5		AM			
		PM			
Day 6		AM			
		PM			
Day 7		AM			
		PM			

COG Patient ID: _____ **ACC # :** _____ **Institution :** _____

Please do not write patient names on this form.

Cycle #:		Start Date: / / /		End Date: / / /	
Dose Level: _____ mg/m ² /dose					
WEEK 2	Date	Time		AM Dose: Take _____ mL	Comments (Describe any missed or extra doses, vomiting and/or bothersome effects.)
				PM Dose: Take _____ mL	
			AM		
			PM		
Day 8			AM		
			PM		
Day 9			AM		
			PM		
Day 10			AM		
			PM		
Day 11			AM		
			PM		
Day 12			AM		
			PM		
Day 13			AM		
			PM		
Day 14			AM		
			PM		

WEEK 3	Date	Time		AM Dose: Take _____ mL	Comments (Describe any missed or extra doses, vomiting and/or bothersome effects.)
				PM Dose: Take _____ mL	
			AM		
			PM		
Day 15			AM		
			PM		
Day 16			AM		
			PM		
Day 17			AM		
			PM		
Day 18			AM		
			PM		
Day 19			AM		
			PM		
Day 20			AM		
			PM		
Day 21			AM		
			PM		

WEEK 4	Date	Time		AM Dose: Take _____ mL	Comments (Describe any missed or extra doses, vomiting and/or bothersome effects.)
				PM Dose: Take _____ mL	
				Amount of oral suspension taken (mL)	
Day 22			AM		
			PM		
Day 23			AM		
			PM		
Day 24			AM		
			PM		
Day 25			AM		
			PM		
Day 26			AM		
			PM		
Day 27			AM		
			PM		
Day 28			AM		
			PM		

If this form will be used as a source document, the site personnel who administered the study drug must sign and date this form below:

Signature: _____
(Site personnel who administered the study drug)

Date: _____

APPENDIX IV: TAZEMETOSTAT DOSING PREPARATION (ORAL SUSPENSION FORMULATION)

Drug doses should be adjusted based on the BSA calculated from height and weight measured within 7 days prior to the beginning of each cycle. Shake the bottle for one minute before you take tazemetostat; do not shake too much if there are bubbles wait for them to dissipate before measuring the dose. Note: If multiple bottles are dispensed, daily shaking of all bottles is required to ensure the suspension stays properly suspended. Store your oral suspension in the refrigerator.

Patients who experience dose-limiting toxicity should have their dose reduced by 25% so that patients receive 75% of the original administered dose. A site-supplied press-in bottle adapter is required for use with an oral syringe for dosing purposes.

Tazemetostat Oral Suspension Preparation Worksheet and Guidance Table

Protocol:	Date of preparation:
Subject ID and Initials:	Cycle #:
BSA (m ²):	
 Assigned dose level: 1200mg/m²/dose BID (Pre-AMD#3) Assigned dose level: 520 mg/m²/dose BID (For patients enrolled post-AMD#3 Patients without CNS involvement see Section 5.1) Assigned dose level: 1200 mg/m²/dose BID (For patients enrolled post-AMD#3 — Patients with CNS involvement see Section 5.1)

Steps:

1) Calculate the mg of tazemetostat required per dose: BSA x dose level	_____ mg per dose BID
2) Calculate the total mg of tazemetostat required per dosing period, including any overfill per institution guidelines* mg per dose x # of doses per day x # of days x overfill (if needed) *An overfill will most likely be needed in order to dispense sufficient quantity to last 14 days	_____ mg per dosing period
3) Calculate total # of grams of tazemetostat required per dosing period. mg from step 2 divided by 1000	_____ grams per dosing period (round up to nearest whole number)
4) Enter # of 2 gram and 7 gram bottles required for dosing period. (refer to the suspension preparation guidance table)	
2 gram bottles: _____
 
7 gram bottles: _____
 
Total # of grams: _____

5) Calculate the total volume of Ora-Sweet® required. Total grams of tazemetostat from step 4 x 32.5 mL/gram	_____ mL (refer to the suspension preparation guidance table)

6) Determine # of empty medication bottles required so that each bottle is filled between 40-80% capacity for adequate mixing. 7) Follow the oral suspension preparation instructions in the protocol.	Bottle #	Grams of tazemetostat	mL of Ora-Sweet® to add	
8) Calculate the volume required per dose mg per step 1 divided by 30 mg/ml	_____ mL per dose BID			

Suspension preparation guidance table:

Total tazemetostat required	2 gm bottles	7 gm bottles	Ora-Sweet® volume* (mL)	Allowable medication bottle size** (mL)
< 2 grams	1	0	65	100-150
2 to <4 grams	2	0	130	200-300
4 to <6 grams	3	0	195	250-500
6 to <7 grams	0	1	228	250-500
7 to <9 grams	1	1	293	400-700
9 to <11 grams	2	1	358	400-800
11 to <12 grams	3	1	[contact]
12 to <14 grams	0	2	[contact]
14 to <16 grams	1	2	[contact]
16 to <18 grams	2	2	[contact]
18 to <20 grams	3	2	[contact]
20 to <21 grams	0	3	[contact]
21 to <23 grams	1	3	748	1000-1800
23 to <25 grams	2	3	813	1000-2000
25 to <27 grams	3	3	878	1100-2100
27 to <28 grams	0	4	910	1200-2400
28 to <30 grams	1	4	975	1300-2500
30 to <32 grams	2	4	1040	1400-2600
32 to <34 grams	3	4	1105	1500-2800
This table is for guidance purposes only, larger volumes should be calculated using the Tazemetostat Oral Suspension Preparation Worksheet .				

*The volume of Ora-Sweet® to obtain a concentration of 30 mg tazemetostat/mL of suspension accounts for the volume of tazemetostat in the solution.

** Total volume listed may require more than one medication bottle to accommodate. Each medication bottle must be prepared separately but multiple whole bottles of tazemetostat powder for oral suspension can be combined into one medication bottle.

APPENDIX V: APEC1621C THERAPY DELIVERY MAP

Therapy Delivery Map – Cycle 1 This Therapy Delivery Map (TDM) relates to Cycle 1. Each cycle lasts 28 days.	Patient COG ID number Accession number
--	---

Criteria to start each cycle are listed in [Section 5.2](#). Extensive treatment details are in [Section 5.1](#).

DRUG	ROUTE	DOSAGE	DAYS	IMPORTANT NOTES
Tazemetostat IND # 134661	PO	Please circle one: -1200 mg/m ² /dose BID (Pre-Amendment #3B) -Patient without CNS involvement: 520 mg/m ² /dose BID -Patient with CNS involvement: 1200 mg/m ² /dose BID Refer to the dosing preparation Appendix IV .	1-28	Tazemetostat will be administered as a liquid suspension orally given twice a day without regard to meals with no less than 8 hours between each dose. If vomiting occurs after taking oral suspension formulation, the dose should NOT be repeated and the next dose should be administered at the regularly scheduled time. See Section 9.1.6 and Appendix IV for additional oral suspension administration and preparation instructions.

Ht _____ cm Wt _____ kg BSA _____ m² Patient with CNS involvement: Yes/No (please circle 1)

Date Due	Date Given	Day	Tazemetostat mg AM mg PM	Studies
			Enter calculated dose above and actual dose administered below	
		1	mg AM mg PM	
		2	mg AM mg PM	
		3	mg AM mg PM	
		4	mg AM mg PM	
		5	mg AM mg PM	
		6	mg AM mg PM	
		7	mg AM mg PM	
		8	mg AM mg PM	a, c, d, e, h
		9	mg AM mg PM	
		10	mg AM mg PM	
		11	mg AM mg PM	
		12	mg AM mg PM	
		13	mg AM mg PM	
		14	mg AM mg PM	
		15	mg AM mg PM	a, c, d, e, h
		16	mg AM mg PM	
		17	mg AM mg PM	
		18	mg AM mg PM	
		19	mg AM mg PM	
		20	mg AM mg PM	
		21	mg AM mg PM	

Cycle 1

		22	mg AM	mg PM	a, c, d, e, h
		23	mg AM	mg PM	
		24	mg AM	mg PM	
		25	mg AM	mg PM	
		26	mg AM	mg PM	
		27	mg AM	mg PM	
		28/1	mg AM	mg PM	a, b, c, d, e, f, h, i, j*,k

See [Section 6.0](#) for Dose Modifications for Toxicities and the COG Member website for Supportive Care Guidelines.

Required Observations in Cycle 1

All baseline studies must be performed prior to starting protocol therapy unless otherwise indicated below. For information related to prestudy observations please refer to [Section 8.1](#). Studies on Day 28/1 may be obtained within 72 hours prior to the start of the subsequent cycle.

a.	History/Physical Exam (including VS)
b.	Ht/Wt/BSA
c.	CBC/differential/platelets- If patients have Grade 4 neutropenia then CBCs should be checked at least every other day until recovery to Grade 3 or until meeting the criteria for dose limiting toxicity. Automated differentials acceptable unless concern for blasts; then please obtain manual differential.
d.	Electrolytes including Ca⁺⁺, PO₄, Mg⁺⁺
e.	Creatinine, ALT, bilirubin
f.	Albumin
g.	Bone Marrow Aspirate and/or biopsy- Only required in patients suspected of having bone marrow metastasis on the basis of history, symptoms, laboratory evaluation or other clinical data. Should only be performed on patients with known bone marrow involvement at baseline. Bone marrow aspirate and/or biopsy should be performed only when complete response or partial response is identified in target disease or when progression in bone marrow is suspected
h.	Medication Diary- (see Appendix III-A and Appendix II-B) should be reviewed after completion of each treatment cycle and uploaded into RAVE. The medication diary should be collected weekly.
i.	Bromide Level
j.	Plain radiograph tibial growth plate (Bone X-Ray Tests). Plain radiographs of at least one tibial growth plate should be obtained in all patients prior to first dose of protocol therapy. In patients with open growth plates, follow-up plain radiographs of the same growth plate(s) should be obtained according to Section 8.2 .
k.	Neurological Exam.

This listing only includes evaluations necessary to answer the primary and secondary aims. OBTAIN OTHER STUDIES AS REQUIRED FOR GOOD CLINICAL CARE.

Comments

(Include any held doses, or dose modifications)

Treatment Details: Cycle 1

Following completion of this cycle, the next cycle starts on Day 29 or when the criteria in [Section 5.2](#) are met (whichever occurs later).

Cycle 1

All Subsequent Cycles

Therapy Delivery Map – All Subsequent Cycles This Therapy Delivery Map (TDM) relates to all subsequent cycles. Each cycle lasts 28 days. Treatment may continue in the absence of disease progression or unacceptable toxicity. Use a copy of this page once for each cycle (please note cycle number below).	Patient COG ID number Accession number
---	---

Criteria to start each cycle are listed in [Section 5.2](#). Extensive treatment details are in [Section 5.1](#).

DRUG	ROUTE	DOSAGE	DAYS	IMPORTANT NOTES
Tazemetostat IND # 134661	PO	Please circle one: -1200 mg/m ² /dose BID (for patients enrolled pre-amendment #3B) -Patient without CNS involvement: 520 mg/m ² /dose BID (only for patients enrolled post-amendment #3B) -Patient with CNS involvement: 1200 mg/m ² /dose BID (only for patients enrolled post-amendment #3B) Refer to the dosing preparation Appendix IV .	1-28	Tazemetostat will be administered as a liquid suspension orally given twice a day without regard to meals with no less than 8 hours between each dose. If vomiting occurs after taking oral suspension formulation, the dose should NOT be repeated and the next dose should be administered at the regularly scheduled time. See Section 9.1.6 and Appendix IV for additional oral suspension administration and preparation instructions.

Subsequent Cycles

Ht _____ cm Wt _____ kg BSA _____ m² Patient with CNS involvement: y/n (please circle 1)

Date Due	Date Given	Day	Tazemetostat mg AM mg PM	Studies
			Enter calculated dose above and actual dose administered below	
		1	mg AM mg PM	a-g, m, n, k
		2	mg AM mg PM	
		3	mg AM mg PM	
		4	mg AM mg PM	
		5	mg AM mg PM	
		6	mg AM mg PM	
		7	mg AM mg PM	
		8	mg AM mg PM	
		9	mg AM mg PM	
		10	mg AM mg PM	
		11	mg AM mg PM	
		12	mg AM mg PM	
		13	mg AM mg PM	

	14	mg AM	mg PM	
	15	mg AM	mg PM	
	16	mg AM	mg PM	
	17	mg AM	mg PM	
	18	mg AM	mg PM	
	19	mg AM	mg PM	
	20	mg AM	mg PM	
	21	mg AM	mg PM	
	22	mg AM	mg PM	
	23	mg AM	mg PM	
	24	mg AM	mg PM	
	25	mg AM	mg PM	
	26	mg AM	mg PM	
	27	mg AM	mg PM	
	28/1	mg AM	mg PM	a-g, h*, j*, k*, l* m, n

See [Section 6.0](#) for Dose Modifications for Toxicities and the COG Member website for Supportive Care Guidelines

* Please refer to [Section 8.1](#) for the specific timing of these observations. Studies on Day 28/1 may be obtained within 72 hours prior to the start of the subsequent cycle.

Required Observations in All Subsequent Cycles

a.	History/Physical Exam (including VS)
b.	Neurological Exam
c.	Ht/Wt/BSA
d.	CBC/differential/platelets If patients develop Grade 4 neutropenia then CBCs should be checked every 3 to 4 days until recovery to Grade 3. Automated differentials acceptable unless concern for blasts; then please obtain manual differential.
e.	Electrolytes including Ca++, PO4, Mg++
f.	Creatinine, ALT, bilirubin
g.	Albumin
h.	Tumor Disease Evaluation – Every other cycle x 3 then q 3 cycles. Tumor Disease Evaluation should be obtained on the next consecutive cycle after initial documentation of either a PR or CR. Subsequent scans may restart 2 cycles after the confirmatory scan. If the institutional investigator determines that the patient has progressed based on clinical or laboratory evidence, he/she may opt not to confirm this finding radiographically.
i.	Bone Marrow Aspirate and/or biopsy- Only required in patients suspected of having bone marrow metastasis on the basis of history, symptoms, laboratory evaluation or other clinical data. Should only be performed on patients with known bone marrow involvement at baseline.
j.	Circulating Tumor DNA (ctDNA-optional) - With consent, two samples will be collected on this protocol (Cycle 5 Day 1; and for patients receiving ≥ 5 cycles, at progression or end of protocol therapy) see Section 8.4 for details of the ctDNA studies.
k.	Plain radiograph tibial growth plate (Bone X-Ray Tests). Plain radiographs of at least one tibial growth plate should be obtained in all patients prior to first dose of protocol therapy. In patients with open growth plates, follow-up plain radiographs of the same growth plate(s) should be obtained according to Section 8.2 .
l.	EKG.
m.	Medication Diary- (see Appendix III-A and Appendix-B) should be reviewed after completion of each treatment cycle and uploaded into RAVE.
n.	Bromide Level

This listing only includes evaluations necessary to answer the primary and secondary aims. OBTAIN OTHER STUDIES AS REQUIRED FOR GOOD CLINICAL CARE.

Comments

(Include any held doses, or dose modifications)

Treatment Details: Subsequent Cycles

Following completion of this cycle, the next cycle starts on Day 29 or when the criteria in [Section 5.2](#) are met (whichever occurs later).

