6.2 Dose Modifications for Hematological Toxicity

- 6.2.1 If a patient experiences hematological dose-limiting toxicity as defined in [Section 5.4.2](#), the treatment will be held. Counts should be checked every 3-4 days for thrombocytopenia and every other day for neutropenia during this time. If the toxicity resolves to meet eligibility parameters within 14 days of drug discontinuation, the patient may resume treatment at a reduced dose (See [Appendix IV](#)). Patients who experience dose-limiting toxicity should have their dose reduced by 25% so that patients receive 75% of the original administered dose (Patients enrolled at 1200mg/m²/dose should dose reduce to 900 mg/m²/dose and patients enrolled at 520mg/m²/dose should dose reduce to 390 mg/m²/dose) Doses reduced for toxicity will not be re-escalated, even if there is minimal or no toxicity with the reduced dose.
- 6.2.2 If toxicity does not resolve to meet eligibility parameters within 14 days of drug discontinuation, the patient must be removed from protocol therapy.
- 6.2.3 If hematological dose-limiting toxicity recurs in a patient who has resumed treatment at the reduced dose, the patient must be removed from protocol therapy.

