8.0 EVALUATIONS/MATERIAL AND DATA TO BE ACCESSIONED

8.1 Required Clinical, Laboratory and Disease Evaluation

All clinical and laboratory studies to determine eligibility must be performed within 7 days prior to enrollment unless otherwise indicated. Laboratory values used to assess eligibility (see [Section 4.0](#)) must be no older than seven (7) days at the start of therapy. Laboratory tests need **not** be repeated if therapy starts **within** seven (7) days of obtaining labs to assess eligibility. If a post-enrollment lab value is outside the limits of eligibility, or laboratory values are older than 7 days, then the following laboratory evaluations must be re-checked within 48 hours prior to initiating therapy: CBC with differential, bilirubin, ALT (SGPT) and serum creatinine. If the recheck is outside the limits of eligibility, the patient may not receive protocol therapy and will be considered off protocol therapy. Imaging studies, bone marrow aspirate and/or biopsy, must be obtained within 14 days prior to start of protocol therapy (repeat the tumor imaging if necessary).

STUDIES TO BE OBTAINED	Pre-Study	During Cycle 1	Prior to Subsequent Cycles [^]
History	X	Weekly	X
Physical Exam with vital signs	X	Weekly	X
Neurologic Exam	X		X
Height, weight, BSA	X		X
Performance Status	X		
Pregnancy Test ¹	X		
CBC, differential ¹⁰ , platelets	X	Weekly ^{2,3}	X ^{2,3}
Urinalysis	X		
Electrolytes including Ca ⁺⁺ , PO ₄ , Mg ⁺⁺	X	Weekly	X
Creatinine, ALT, bilirubin	X	Weekly	X
Albumin	X		X
Bromide Level	X		X
INR	X		
EKG	X		Every 3 cycles
Tumor Disease Evaluation ^{4-A, 4-B, 4-C}	X		Every other cycle x 3 then q 3 cycles ⁴
Bone Marrow Aspirate and/or biopsy ^{5,6}	X		
Plain radiograph tibial growth plate (Bone X-Ray Tests) ⁹	X		Prior to cycles 2, 5 and every 6 months
Patient Diary ⁷		Weekly	X
Circulating Tumor DNA (ctDNA-optional) ⁸			Cycle 5, Day 1 and (for patients receiving ≥ 5 cycles only) at end of Protocol Therapy OR disease progression

[^] Studies may be obtained within 72 hours prior to the start of the subsequent cycle.

¹ Women of childbearing potential require a negative pregnancy test prior to starting treatment; sexually

- active patients must use an acceptable method of birth control. Abstinence is an acceptable method of birth control.
- 2 If patients have Grade 4 neutropenia then CBCs should be checked at least every other day until recovery to Grade 3.

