 - 3 If patients develop Grade 3 or greater thrombocytopenia then CBCs should be checked every 3 to 4 days until recovery to Grade 3, per [Section 6.1](#).
 - 4 Tumor Disease Evaluation should be obtained on the next consecutive cycle after initial documentation of either a PR or CR. Subsequent scans may restart 2 cycles after the confirmatory scan. Please note that for solid tumor patients, if the institutional investigator determines that the patient has progressed based on clinical or laboratory evidence, he/she may opt not to confirm this finding radiographically.
 - 4-A Neurological exam also required for CNS patients.
 - 4-B Non- Hodgkin Lymphoma/ Histiocytosis patients are required to have PET scans within 2 weeks prior to start of therapy and should also be followed with PET scans if positive at diagnosis. Refer to [Section 12.8](#).
 - 4-C Patients with neuroblastoma must have both CT/MRI and MIBG scintigraphy prior to enrollment if the patient was enrolled with or has a history of having MIBG avid tumor. Otherwise the patient must have both CT/MRI and bone scan prior to enrollment. For patients with neuroblastoma and measurable disease by CT or MRI, lesions should be measured and followed using the same modality (CT or MRI) in addition to MIBG or bone scan. For patients with neuroblastoma and evaluable disease by MIBG scintigraphy or bone scan, use the same modality (MIBG scintigraphy or bone scan) to image and follow patients; CT/MRI are not required but may be performed as clinically indicated. Refer to [Section 12.5.4](#) and [Section 12.9](#).
 - 5 Bone marrow aspirate and/or biopsy only required in patients suspected of having bone marrow metastasis on the basis of history, symptoms, laboratory evaluation or other clinical data. Should only be performed on patients with known bone marrow involvement at baseline.
 - 6 Bone marrow aspirate and/or biopsy should be performed only when complete response or partial response is identified in target disease or when progression in bone marrow is suspected.
 - 7 Patient diary (see [Appendix III](#)) should be reviewed weekly during Cycle 1 and then after completion of each treatment cycle and uploaded into RAVE.

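### The later-cycle map sets too long a CBC interval for Grade 4 neutropenia, and the Section 8.1 platelet recheck rule stops at the grade that starts it

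*Combined protocol and SAP*

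**What the plan says.** **Grade 4 neutropenia**

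- Appendix V, All Subsequent Cycles, item d: "If patients develop Grade 4 neutropenia then CBCs should be checked every 3 to 4 days until recovery to Grade 3".
- Section 8.1 footnote 2: "If patients have Grade 4 neutropenia then CBCs should be checked at least every other day until recovery to Grade 3". The Section 8.1 table attaches this footnote to the CBC row both for Cycle 1 and for later cycles.
- Section 6.2.1, during a hold for a hematological DLT: "Counts should be checked every 3-4 days for thrombocytopenia and every other day for neutropenia during this time".
- Appendix V, Cycle 1, item c uses the footnote 2 interval but adds a second stopping point: "CBCs should be checked at least every other day until recovery to Grade 3 or until meeting the criteria for dose limiting toxicity".

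**Thrombocytopenia**

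- Section 8.1 footnote 3: "If patients develop Grade 3 or greater thrombocytopenia then CBCs should be checked every 3 to 4 days until recovery to Grade 3". It refers the reader to Section 6.1, which deals with newly diagnosed T-LBL/T-ALL. Hematological toxicity is in Section 6.2.
- Neither Appendix V map carries a platelet recheck rule.

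**What depends on these counts**

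- Section 5.4.2, for patients evaluable for hematological toxicity, makes a DLT of Grade 4 neutropenia not due to malignant infiltration, and of Grade 3 thrombocytopenia lasting 7 days or more.
- Section 6.2.1 then requires a hold and a lower dose: "Patients who experience dose-limiting toxicity should have their dose reduced by 25% so that patients receive 75% of the original administered dose".
- Section 4.1.6.1.b makes patients with known marrow metastases eligible but not evaluable for hematologic toxicity.

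**The concern.** Item d and footnote 2 have the same trigger, the same recovery point and the same cycles, but different intervals. Elsewhere in the plan the 3-to-4-day interval belongs to platelets, so item d looks like a transposition rather than a deliberate relaxation. It matters in practice because the map is the site's working sheet for every later cycle ("Use a copy of this page once for each cycle").

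Footnote 3 has a logical fault. Its stopping condition is already met by a patient who has just triggered it at Grade 3. One of the hematological DLTs is defined by how long Grade 3 lasts, and duration cannot be established without repeat counts. At stake are a DLT and its dose reduction in a child still on drug. Tolerability (Section 1.2.2) is also a secondary aim, and Section 11.4 records onset and resolution times. The worst-grade toxicity table is less exposed, because the count that triggers the rule already records Grade 3.

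**Working it through.** The plan states no figure to reproduce. The check sets the rules side by side and adds simple interval arithmetic.

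**Part 1: Grade 4 neutropenia**

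| Rule | Applies to | Longest gap | Ends at |
|---|---|---|---|
| 8.1 footnote 2 | Cycle 1 and later cycles | 2 days | Grade 3 |
| 6.2.1 | Any hold for a hematological DLT | 2 days | Eligibility levels within 14 days, or removal |
| Appendix V Cycle 1, item c | Cycle 1 | 2 days | Grade 3, or DLT criteria met |
| Appendix V later cycles, item d | Cycles 2 to 26, i.e. 25 of 26 possible | 4 days | Grade 3 |

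Which rule reaches which patient:

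1. *Evaluable for hematological toxicity, not due to infiltration.* Grade 4 neutropenia is a DLT at once (5.4.2). The later-cycle map sends the reader to Section 6.0 for dose modifications, so 6.2.1 applies and counts are every other day.
2. *Known marrow disease.* The event is not a DLT under 5.4.2, so 6.2.1 is not triggered. Only footnote 2 and item d set a frequency, and they disagree. The map's asterisk, which sends the reader to Section 8.1 "for the specific timing of these observations", is on items h, j, k and l, not on d.

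**Part 2: Grade 3 thrombocytopenia**

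1. Grades that start footnote 3: {3, 4}. Grades that stop it: {3 or lower}. They overlap at Grade 3. The rule works for Grade 4, which is followed down to Grade 3, and sets nothing for a patient who is only ever Grade 3.
2. *Evident intent.* Call the triggering count day 0 and step by 3 or 4 days. The first count on or after day 7 falls on day 7 (3+4), 8 (4+4), 9 (3+3+3) or 10 (3+3+4), which is enough to establish a 7-day episode soon after it qualifies.
3. *Cycle 1 as scheduled.* Counts fall on days 8, 15, 22 and 28/1, about 7 days apart. Grade 3 on day 8 and again on day 15 documents 7 days without footnote 3. Cycle 1 is largely covered.
4. *Later cycles as scheduled.* Counts fall only at cycle boundaries, nominally 28 days apart. Each may be drawn up to 72 hours early, so the gap runs from 28 − 3 = 25 to 28 + 3 = 31 days.
5. *What can be missed from Cycle 2.* If Grade 3 is found at a boundary, Section 5.2 bars the next cycle until eligibility laboratory levels are met again, but it sets no recheck interval. A delay of more than 14 days is itself a DLT. That leaves episodes of about 7 to 14 days: long enough to be a DLT by duration, too short to be caught by the delay criterion. If Grade 3 is found on an unscheduled mid-cycle count, the next required count is the boundary one.
6. An episode that starts and ends between boundary counts with no count taken is unseen under either wording. The fix addresses only episodes that some count has picked up.

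**The case against.** The strongest reply is that these are copy-editing slips with other safeguards around them, and much of that stands.

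- For neutropenia, a reader might infer that no text settles the conflict for anyone. The documents do not support that. The map's pointer to Section 6.0 leads evaluable patients to 6.2.1 and its every-other-day counts. For the same reason item d does not halve monitoring during a 14-day hold.
- For platelets, a reader might infer that Grade 3 patients have no repeat counts anywhere in the trial. Weekly CBCs in Cycle 1 rule that out.
- In later cycles, Section 5.2 blocks the next cycle, and long delay, significant bleeding or platelet transfusion on two days within a week are separate DLT criteria. The map also tells sites to obtain whatever else good care requires. Most sites would probably recheck a Grade 3 platelet count unprompted.
- Section 5.3 (suspected DLTs to the Study Chair within 24 hours) and the weekly leadership call in Section 14.4.2 also help, but they act on counts already taken and do not require one.
- The wrong reference to Section 6.1 is editorial, with no consequence shown.

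What remains is that, before a DLT is met, footnote 3 is the only rule from Cycle 2 that sets a platelet recheck interval, and it sets none at Grade 3. The intent is plain, but the text does not deliver it.

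**Conclusion.** Both rules are wrong as written, and the point is minor. Item d allows gaps of up to 4 days instead of 2. The conflict is unresolved mainly for patients with known marrow disease. Footnote 3, read literally, gives no repeat counts to a patient who is only ever at Grade 3. The practical gap is from Cycle 2 on, where a 7-to-14-day episode and its 25% dose reduction could be missed if the site does not recheck on its own initiative.

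The number of patients affected is not given. A reader might take the CAEPR band for platelet or neutrophil count decreased (20% or less, 815 patients) and compute 0.20 × 49 = 9.8, so about 10 patients at most for each event. That is not a ceiling. The band covers events possibly related to the drug, whereas the CBC rules apply to low counts from any cause. Nor does it separate Grade 3 or 4 from lower grades, or identify patients with marrow disease.

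The conclusion rests on a literal reading of footnote 3 and on sites doing no more than the scheduled counts. The primary endpoint, the sample size and the decision rule are unaffected.

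**What to change.** - **Appendix V, All Subsequent Cycles, item d:** change the interval for Grade 4 neutropenia to at least every other day.
- **Section 8.1 footnote 3:** continue counts every 3 to 4 days until recovery to Grade 2 or lower, and cite Section 6.2 instead of 6.1. Section 6.2.1 continues to govern recovery to eligibility levels during a DLT hold.
- **Appendix V, Cycle 1 item c and later-cycle item d:** refer to Section 8.1 footnotes 2 and 3 rather than stating separate rules. This brings the platelet rule into both maps. It also removes item c's extra stop at meeting DLT criteria, which an evaluable patient with Grade 4 neutropenia not due to infiltration meets immediately.

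Footnote 2 and Section 6.2.1 need no change. The cost is a few words and a few extra CBCs for affected patients, with no effect on sample size, endpoint or analysis.
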